4.7 Packaging

Study drug and inert placebo will be shipped from supplier in bulk containers and stored in the investigational drug pharmacy.

4.8 Blinding of Study Drug (if applicable)

Only the investigational drug services and unaffiliated staff will know the contents of the capsules. The study drugs and comparator will be packaged in identical capsules and will be indistinguishable. Each participant will be assigned to a treatment arm using randomize.net. Randomization will be accomplished via randomize.net. A Randomization ID will be generated that corresponds to the treatment. Only the IDS will dispense the study drug maintaining strict blinding.

4.9 Receiving, Storage, Dispensing and Return

4.9.1 Receipt of Drug Supplies

The drug supplier will ship the study drug and comparator to the Investigation Drug Pharmacy. Once the study drug arrives, receipt of the study drug will be performed. A drug receipt log will be completed and signed by the person accepting the shipment. Each site will develop their own process for maintaining a log of drug administration. The designated study staff will count and verify that the shipment contains all the items noted in the shipment inventory supplied at the time of shipment. Any damaged or unusable study drug in a given shipment (active drug or comparator) will be documented in the study files.

4.9.2 Storage

Drug will be stored at 77 degrees Fahrenheit with excursions permitted from 59-86 degrees Fahrenheit at the investigational drug pharmacy. At each site, it will be kept in a climate-controlled room. The drug will not be frozen. There is no requirement for the drug to be shielded from light or any other special requirements.

4.9.3 Dispensing of Study Drug

The study drug will be dispensed by ED nursing staff. Study drug reconciliation will be performed at the conclusion of the study. This reconciliation will be logged on the drug accountability form and signed and dated by the study team. This log will be kept by the site investigational drug pharmacy and via the REDCap data collection software being used in this study.

4.9.4 Return or Destruction of Study Drug

At the completion of the study, there will be a final reconciliation of drug shipped, drug consumed, and drug remaining. This reconciliation will be logged on the drug reconciliation form, signed and dated. Any discrepancies noted will be investigated, resolved, and documented prior to return or destruction of unused study drug. Drug destroyed on site will be documented in the study files.

Study Procedures

5.1 Enrollment Procedures

This first visit will take place upon admission to the hospital following MVC within 24 hours of the collision. Patients who meet inclusion criteria/exclusion criteria based on a review of the electronic medical record by research assistants, participants will be approached for participation. If the patient is interested in participating, they will then undergo informed consent. At this point in time, the participants will undergo baseline assessments (administered through REDCap) and collections of point of care Vitamin D levels with blood spot card. The participants will also have the option to consent to collect additional blood during a standard of care procedure while in the ED. The study would collect an EDTA tube,

a sodium heparin tube, and PAX gene RNA and DNA tubes. Patients with a Vitamin D level <100 ng/ml, will then take the baseline questionnaire. After all baseline data is collected, participants will be randomized and then administered appropriate study medication (Vitamin D or placebo). This administration will be documented in the MAR. Patients will be given a paper copy of their consent. Upon discharge of the patient, the patient will be given supplies to perform a home fingerstick blood draw (similar to one collected in the ED for baseline) and blotting on a blood spot card, which will occur at the 3-month timepoint.

Medical record information abstracted at time of admission will include information related to patient past medical history and initial motor vehicle collision care, and medication use prior to admission and prior to enrollment. Laboratory values relevant to patient renal and hepatic function will also be recorded (if obtained) along with any toxicology labs obtained by the primary treating team.

Demographic and phenotypic data will be collected at this time. Patients will be asked to report demographic information including age, sex, ethnicity, education level, income level, and marital status. In addition, patients will be administered an enrollment survey which will collect domains important to the pain experience. These are listed in table 2. All patient information will be recorded by a trained research assistant or the patient via direct entry. We will assess treatment expectation using a modified survey that uses Likert scales prior randomization. In addition, we will administer weekly surveys of pain severity and to assess whether adverse events are experienced weekly through 6 weeks (these brief surveys will be sent at 2 weeks, 4 weeks and 5 weeks). Adverse events will also be monitored at 3 weeks, 6 weeks, and 3 months following administration of study drug.

Table 2. Assessments by domain at each timepoint

Domain	Measure	D1	3W	6W	3M
Demographic information	Age, sex, gender, race/ethnicity, education, income, marital status	●			
Pre-MVC	Pain catastrophizing scale ²⁶ , PROMIS Item Bank v1.0 - Emotional Distress – Anxiety ²⁷ , PROMIS Item Bank v1.0 - Emotional Distress - Depression ²⁷ , Anxiety Sensitivity Index ⁵¹	●	●	●	●
Traumatic Event	Details of Traumatic Event, Concussion, Traumatic Brain Injury, Life events checklist ²⁸	●			
MVC Injury Severity	Abbreviated injury scale ²⁹	●			
Pain	Numeric Rating Scale, [†] RPS ³⁰ , PROMIS Short Form v1.0 - Pain Interference 4a ³¹ , PROMIS Scale v2.0 - Neuropathic Pain Quality 5a ³² , PROMIS Scale v2.0-Nociceptive Pain Quality 5a	●	●	●	●
Somatic Symptoms	Pennebaker Inventory of Limbic Languidness ⁵²	●	●	●	●
Global Mental and Physical Health	PROMIS Scale v1.2 - Global Mental 2a ³³ , PROMIS Scale v1.2 - Global Physical 2a ^{33,34}	●	●	●	●

Anxiety/Depressive Symptoms	PROMIS Item Bank v1.0 - Emotional Distress – Anxiety ²⁷ , PROMIS Item Bank v1.0 - Emotional Distress - Depression ²⁷	●	●	●	●
Posttraumatic stress symptoms	PTSD Symptom Severity index-interview for DSM-5 ³⁵ , Peritraumatic Distress Inventory items (PDI) ⁵³	●	●	●	●
Dissociative Symptoms	Michigan Critical Events Perception Scale ³⁶	●			
Analgesic Medication Use	Daily milligram morphine equivalents, non-opioid analgesic use, Date of opioid cessation (first day in three consecutive where patient took no opioids) ³⁷ .	●	●	●	●
Substance abuse	PROMIS Short Form v1.0 - Severity of Substance Use (Past 30 days) 7a ³⁸	●	●	●	●
Patient satisfaction with treatment	Patient Global Impression of Change ³⁹		●	●	●

At the time of enrollment, blood for DNA will be collected using a PAXgene DNA storage tube (8.5cc). These samples will be stored at -70 °C or below for future testing. Blood for RNA will be collected using a PAXgene RNA storage tube (2.5cc). These samples will be stored at -70 °C or below for future testing. Blood for immune profiling will be collected in sodium heparin tubes (16cc). Whole blood collected from sodium heparin tubes will be aliquoted into SmartTubes which allow storage for later processing by mass cytometric methods. Additional aliquots from these tubes will be used to assess adaptive and innate immune function in vitro. Blood for lipidomics, vitamin D level and protein expression analysis will be obtained via EDTA tubes containing K₂EDTA for sample anticoagulation (8cc). Plasma will be separated from the cells by centrifuging the collection tube for 10 minutes at 2000 rpm at 25 °C, within two to 48 hours of collection. Plasma will be stored in 100-250 µL aliquots in plastic microcentrifuge tubes at -70 °C or below for future testing. Total amount of blood collected via venipuncture will be 35-36cc. A drop of blood will be applied to a dried blood spot cards for Vitamin D testing.

5.2 Emergency Department Medication Administration

The single dose administration will be provided in an observed fashion in the emergency department. This administration will be recorded in the patient's electronic medical record in the medication administration record (MAR).

5.3 Data Extraction

Medical record information abstracted after discharge will include information on the patient's health status and care during hospitalization and at the time of discharge. This information will include MVC characteristics, medications taken during emergency department admission, and discharge medications. All data extraction will be stored in REDCap.

5.4 Text messaged or e-mailed outpatient Weekly Pain and Compliance Assessments

Brief, weekly assessments of pain severity (0-10 NRS), and review of any AEs over the past week will occur via e-mailed surveys administered through our secure study database REDCap. Patients will receive text messages from the Data Coordinating Center based on a predetermined schedule based on progress, using the secure study phone number. If

patients are not able to respond via text messaging or e-mail, they will be called by investigative team. This brief survey will be administered at 2 weeks, 4 weeks, and 5 weeks.

5.5 3- and 6-week assessment

The goal of this assessment is to perform a comprehensive phenotypic follow-up and a questionnaire assessing domains listed in table 2 will be assessed. Outcome assessments will be performed via structured survey either via a web-based Redcap survey emailed to their on-file email address or via telephone. Multiple methods of contacting participants are involved to best meet the needs of each individual participant. Patients will receive automated REDCap email reminders. Participants will also receive text reminders based on a predetermined schedule based on progress. If patients are not able to respond via text messaging or e-mail, they will be called by investigative team.

5.6 3-month assessment

The goal of this assessment is to perform a comprehensive phenotypic follow-up and a questionnaire assessing domains listed in table 2 will be assessed. Outcome assessments will be performed via structured survey either via a web-based Redcap survey emailed to their on-file email address or via telephone. Multiple methods of contacting participants are involved to best meet the needs of each individual participant. Patients will receive automated REDCap email reminders, and text message reminders sent on a predetermined schedule based on progress. If patients are not able to respond via text messaging or e-mail, they will be called by investigative team. In addition, the patient will obtain a blood sample blotted onto a blood spot card acquired via a fingerstick at the 3-month mark of their study participation (achieved with a sterile lancet mailed to the participant at the 2-month timepoint of study participation). The completed sample card will be mailed via a self-addressed envelope to the central processing laboratory. All materials and education to conduct this blood draw will be mailed to participants and patients will be reminded this procedure at the 3-month follow-up. If the participant loses the materials, they will be re-shipped to the participant from the data coordinating center.

Statistical Plan

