3.2 Study Overview

Described the sequence of events in recruiting 90 patients in a multi-center randomized controlled trial. To assess a key primary outcome, we will enroll 50% white and 50% black MVC into the study. Each participant will be screened in based on a point of care Vitamin D test. This will be performed at the time of screening. Individuals with a Vitamin D level <100 ng/ml will be enrolled. Patients will be randomized 1:1 to receive a single dose of 300,000 IU of ergocalciferol versus placebo and followed for 3 months. At 3 months, patients will send a blood sample easily collected at home on a blood spot card to assess Vitamin D level 3 months following injury which is a key feasibility primary outcome.

Patients presenting to the ED within 24 hours of MVC (n=90, 45 non-Hispanic Black, and 45 non-Hispanic White) will receive a single dose of study drug prior to ED discharge (1:1 allocation 300,000 IU ergocalciferol or placebo). Prior to study drug administration, a baseline assessment will be performed (see below), and a fingerstick blood sample will be obtained to evaluate 25-hydroxyvitamin D level. Online survey follow-ups assessing primary and secondary outcomes and potential adverse events will be performed 3 weeks, 6 weeks, and 3 months after ED enrollment by study RAs using web-based REDCap™ software. Participants will also complete brief “flash-surveys” at the 2-week, 4-week, and 5-week timepoints using REDCap survey links. At 3 months, participants will also perform a fingerstick blood collection at home and mail the sample in a prepaid envelope to a lab to be processed to enable assessment of 3 month 25-hydroxyvitamin D concentration by treatment group.

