study site PI(s), and other investigators. The DCC PI will monitor for adverse events that change study risk level and this will be communicated with the independent medical monitor if needed. Adverse events at individual study sites will also be monitored by the site PI. If an adverse event occurs which changes the study risk level, the DCC PI will immediately report this event to the DCC IRB (UNC IRB), inform the site PI(s), and oversee the process of modifying the study at the study site(s) as appropriate to address the change in risk. The DCC PI will also provide annual reports summarizing AE data to the data coordinating center IRB (UNC IRB) and any other requesting IRB. The site PI(s) will oversee patient safety at their site, with delegation of responsibilities to other investigators and designated study personnel as appropriate. The DCC PI, together with their study site teams, will ensure that all entry criteria are met prior to the initiation of the protocol, and that all study procedures and reporting of adverse events are performed according to the protocol. Serious adverse events (SAE's) will be monitored by the study site investigative teams in real time throughout the trial.

Patient monitoring: An adverse event is any physical or clinical change experienced by the patient. This includes the onset of new symptoms and the exacerbation of pre-existing conditions. Adverse event assessments will be performed according to the following schedule:

Adverse event monitoring after discharge from ED: Adverse events will be assessed at each patient contact (telephone or text-messaged/mailed survey), which will occur weekly for 6 weeks, then again at 3 months.

Additional reporting: In addition to receiving these regular side effect assessments, patients will be given contact information to reach the study team at the DCC, as well as telephone and pager numbers for individuals at the study site, and will be instructed to call these numbers if they experience any changes in their health status or if they have questions regarding the study medication.

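### No adverse-event contact is scheduled in week 1 after the single dose, the week-2 survey looks back only one week, and handling of expected non-serious events after day 30 is unclear

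*Combined protocol and SAP*

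**What the plan says.** All references are to the combined protocol and SAP.

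**Contact frequency.** Section 7.6 says that AEs are assessed at every patient contact, "which will occur weekly for 6 weeks, then again at 3 months". Section 5.1 uses the weekly description and a list of dates in one sentence: "whether adverse events are experienced weekly through 6 weeks (these brief surveys will be sent at 2 weeks, 4 weeks and 5 weeks".

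**Scheduled dates.** Section 5.4 sets the brief survey: "This brief survey will be administered at 2 weeks, 4 weeks, and 5 weeks". Section 5.1 adds the full surveys: "Adverse events will also be monitored at 3 weeks, 6 weeks, and 3 months following administration of study drug". Sections 3.2 and 10.3 give the same dates.

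**Look-back.** The only AE window stated anywhere is the one in section 5.4: "Brief, weekly assessments of pain severity (0-10 NRS), and review of any AEs over the past week will occur via e-mailed surveys". Sections 5.5 and 5.6, on the 3-week, 6-week and 3-month surveys, refer to the domains of Table 2, which has no AE row, and give no AE window.

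**Supporting provisions.** Section 7.2 requires direct questioning about AEs at each contact and the recording of every AE in the study period. Section 7.1 starts the AE reporting period with the first study procedure. Under section 7.6, patients "will be instructed to call these numbers if they experience any changes in their health status".

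**End of the period.** Section 7.1 ends the AE reporting period for this study 30 days after the last administration, which here is the only one. Section 3.5 ties AE tracking to the time on drug treatment.

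**The concern.** The drug is given once, in the emergency department. The one weekly contact that is described but not scheduled is the one for the week straight after that dose. A late first contact would matter little if it asked back to dosing, but the written window stops one week short of it.

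The surveys are the stated instrument for the primary safety endpoint (section 3.5). AE reports by type, severity and treatment arm go to the DSMB (section 7.6). A short non-serious event in week 1 could be absent from both. The whole-trial stopping rule in section 7.5 is also touched. It counts patients with related or possibly related events of grade 3 or higher and does not require the event to be serious, so a brief grade 3 non-serious event in week 1 could count toward it and yet not be asked about.

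The second matter is the other end of follow-up. If AEs are collected after the reporting period has closed, sites or the analyst could include or exclude the same event.

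**Working it through.** Dosing is day 0. Three months is taken as day 90, which is my assumption.

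**1. Contacts described and contacts scheduled**

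- Weekly for six weeks (section 7.6): days 7, 14, 21, 28, 35, 42 = 6 contacts.
- Brief surveys (section 5.4): days 14, 28, 35. Full surveys (section 5.1): days 21, 42 and about 90.
- Scheduled within six weeks: days 14, 21, 28, 35, 42 = 5 contacts. The missing one is day 7.
- Cross-check with the payments in section 10.3: 40 + 10 + 3 × 20 + 50 + 55 + 60 + 40 = 315 dollars. This equals the stated maximum, and no item is for week 1.

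The described 6 contacts are not reproduced; the schedule gives 5 of 6.

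**2. Days that no survey is stated to ask about**

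- Week-2 survey with a 7-day window: first day 14 − 7 + 1 = 8, so days 8 to 14.
- Days before that window: 1 to 7, or 7 days. As a share of the 30-day reporting period: 7/30 = 23%.
- The window of the full surveys is not stated, so I varied it for the 3-week survey:

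| Assumed look-back at 3 weeks | Days covered | Days 1–7 not asked about |
|---|---|---|
| 7 days | 15–21 | 7 |
| 14 days | 8–21 | 7 |
| 21 days or more | from day 1 | 0 |

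The range is therefore 0 to 7 days. The same unknown applies at month 3: with a 7-day window that survey covers days 84 to 90, leaving days 43 to 83 (83 − 43 + 1 = 41 days) unasked; with a window back to the last survey, none.

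**3. Which events are exposed**

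An event still present on day 8 or later falls inside the week-2 window. What is left is non-serious events that both begin and resolve in days 1 to 7. Sections 1.2 and 1.4 name mild gastrointestinal complaints as the most common side effect but give no onset times, so no count can be derived.

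**4. Surveys and the day-30 limit**

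- AE surveys after day 30: days 35, 42 and about 90 = 3 of 6.
- Week-5 window: days 29 to 35, of which 29–30 (2 days) lie inside the limit and 31–35 (5 days) outside.

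Recording rules that still apply after day 30:

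| Type of event after day 30 | Provision |
|---|---|
| Serious, possibly related | Section 7.2: record and report |
| Unanticipated, serious or not | Section 7.6: AE form; Table 3 gives a two-week limit for non-serious ones |
| New clinically significant finding at study end | Section 7.1: record |
| Expected and non-serious | No clear rule |

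The last row turns on whether *study period* in section 7.2 means the 30-day reporting period of section 7.1 or the three months of follow-up. The text does not say.

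**The case against.** The best defence is that the week-1 gap is conditional. The survey questions themselves are not in the documents, and the one-week look-back is a single phrase about a survey called weekly. The recording duty is wider. It runs from the first study procedure and covers every AE in the period, so a week-2 contact that ignored days 1 to 7 would sit badly with section 7.2. Patients also have a number to call.

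Part of this stands: the documents do not show that events will be lost. But the duty to record is not a recall window, and none of these provisions sets one back to dosing. The first contact is normally a survey that the participant completes alone, with a telephone call only if "patients are not able to respond via text messaging or e-mail, they will be called by investigative team". Calling in depends on the participant, and a short mild event is plausibly the least likely to prompt a call.

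A second defence is that the consequence is modest. Section 3.5 plans only a qualitative analysis of AEs, and ascertainment is the same in both blinded arms. That also stands. A reader might infer biased safety comparisons between arms; the documents support possible under-counting, not demonstrated bias.

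A third defence concerns day 30. A reader might infer that no non-serious event after day 30 has a recording rule. That goes too far, because sections 7.1 and 7.6 cover new clinically significant findings at study end and unanticipated events.

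**Conclusion.** The point holds in a limited form.

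**Week 1.** The weekly description and the schedule disagree, and this is certain from the text: 5 of 6 contacts, none in week 1. Whether data are missed depends on survey wording that the documents do not give. Following the one stated window leaves 7 days without a survey question; a look-back to dosing at week 2 or week 3 leaves 0. Only non-serious events confined to days 1 to 7 are exposed, in unknown number.

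Two opposite inferences should be avoided. One is that week-1 events will be missed altogether: the call-in route and the recording duty remain. The other is that the whole-trial stopping rule is untouched because section 7.5 has no 30-day limit. That argument answers only the day-30 matter, and a brief grade 3 non-serious event in week 1 remains possible.

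**Day 30.** This is mainly a matter of reconciling text. Three of six AE surveys come after the reporting period closes. What is unsettled is chiefly expected non-serious AEs after day 30, and the meaning of the study period in section 7.2. The reference in section 3.5 to the time on drug treatment does not fit a one-time dose, but that is a point of wording.

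**What to change.** 1. Have the existing week-2 survey ask about AEs since the study capsules were taken. Have each later AE survey, including those at 3 weeks, 6 weeks and 3 months, ask about AEs since the last survey the participant completed. State these windows in sections 5.4 to 5.6. This closes days 1 to 7 and also days 43 to 83, and it still works when a survey is skipped.
2. Reconcile the weekly wording in sections 5.1 and 7.6 with the scheduled contacts. Adding a week-1 contact would also resolve the mismatch, but it is not needed to close the recall gap.
3. Reconcile sections 3.5, 7.1, 7.2 and 7.6 to one AE collection and reporting period, and say how non-serious AEs after day 30 are recorded and counted.

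The cost is recall wording in existing surveys and text edits, with no new contact and no new payment. The drawback is that longer recall is less precise: 14 days at week 2 and 90 − 42 = 48 days at month 3, against one week now stated for the brief surveys.
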